TITLE OF STUDY

Downstream molecular signals of P2Y12 receptors in hyporeactive patients under clopidogrel treatment

NCT03190005 Unique Protocol ID: TCHIRB-10603117-E

PRINCIPAL INVESTIGATOR

[Name] [name]

[Department] Taipei City hospital Division of Cardiovascular section

[Address] [name]

[Phone] [name]

[Email] [contact]

Date: 2017/6/6

Methods

This study enrolled 35 patients(subgroup 1 and subgroup 2) who had undergone elective PCI and stent implantation and were receiving routine dual antiplatelet treatment (aspirin + clopidogrel). The study was registered under ClinicalTrials.gov (ID: NCT03190005) and approved by the Institutional Review Board of the Taipei City hospital Reserch Ethics Committee(ID: TCHIRB-10603117-E)

In subgroup 1

Blood samples were obtained from all study patients, and platelets were separated as previously described. The experimental procedure is described in Supplementary Figure A. PRU values were determined for control patients and for patients treated with DAPT after 7 days of treatment. Based on PRU values, patients were classified

as 1) normal reactive (defined as PRU=85-207), 2) hyporeactive (defined as PRU>208), or 3) hyper-reactive groups (defined as PRU < 85). The Western blot responses were determined for each group after treatment with the different drugs, and these values were represented as a bar graph for statistical and comparative purposes. in-vitro experiments were performed using platelet-rich plasma (PRP) samples which were treated with different combinations of drugs. These included 1) ADP (10 μ M), 2) PGE1 (0.1 μ M), 3) aggrastat (glycoprotein IIb/IIIa receptor inhibitor; 0.25 μ g/ml), 4) AR-C 66096 (P2Y12 receptor antagonist; 1 μ M), 5) OPC-13013 (PDE3A tyrosine kinase inhibitor; 10 μ M). The control group received no drugs. Reactions were terminated by addition of Indomethacin (50 μ M) and EDTA (2 mM) 4 minutes after the drugs were added. Total protein was prepared from untreated and treated samples, and subjected to Western blotting according to standard protocols.

In order to eliminate the effect of liver enzymes, we design subgroup 2:

In this subgroup 2, we developed an ex-vivo system to investigate the role of P2Y12 signaling on HOTPR in patients with different reactivities to DAPT.

PRU measurements

PRU values were determined in 2 ml blood samples using the VerifyNow test (Accumetrics, San Diego, CA, USA) according to the manufacturer's instructions. In this study HOTPR was defined as PRUs \geq 208 as recently described ²¹.

Western blotting

Protein expression was analyzed in PRP samples obtained from patients in the different groups. Briefly, PRP was obtained from 15cc blood after addition of 1.5cc of 3.8% sodium citrate. The samples were centrifuged at 1000 rpm , and complete blood counts were performed on the PRP samples in order to determine the levels of WBC contamination. If the WBC to platelet ratio was > 0.4%, the sample was re-centrifuged at 1000 rpm for 5 minutes repeatedly until the WBC to platelet ratio was < 0.4%. Total protein was prepared from the PRP samples as described. Total proteins were separated by SDS-PAGE, and immunoblotted to evaluate the expression of p-p38, total P38, p-PKC ζ , total PKC ζ , p-Akt/PKB, total AKT, p-GSK3 β , total GSK3 β , p-VASP, total VASP, p-Syk, total syk, P2Y12 receptor, PLC β -1, and Rap1b (Supplementary Table 1). The protein quantifications from western blot images were done using the Image J program (NIH, MD).

CERTIFICATE

Date : May 24, 2017

The project entitled "Downstream molecular signals of P2Y12 receptors in hyporeactive patients under clopidogrel treatment" submitted by investigator [name] has been approved by Research Ethics Committee of the Taipei City Hospital.

Protocol Version Date: Ver1-1060215

ICF Version Date: Ver 2.1-1060524

Study period: since 01/01/2017 to 12/31/2017

Above project is approved by the TCHREC on 05/24/2017 and valid till 12/31/2017.

- ※ All protocols should be subject to final endorsement by the board. TCHREC has the right to revoke the approval.
- ※ No new protocol can be applied if the midterm report or the final report is not handed in.
- ※ The midterm report should be handed in one month before the expiry date of this certificate.
- ※ The final report should be handed in before the expiry date of this certificate or project end.
- ※ The PI should send the amendments to TCHREC at least six weeks before the expiry date of this certificate if there are changes or modification related the protocol. Any change should not be executed until being approved by TCHREC.

[name]

Chairman

Taipei City Hospital Research Ethics Committee

The committee is organized and operates in accordance with ICH-GCP regulations and guideline.

本委員會組織與運作皆遵守 ICH-GCP 規定

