TITLE OF STUDY

Downstream molecular signals of P2Y12 receptors in hyporeactive patients under clopidogrel treatment

NCT03190005 Unique Protocol ID: TCHIRB-10603117-E

PRINCIPAL INVESTIGATOR

[Name] [name]

[Department] Taipei City hospital Division of Cardiovascular section

[Address] [name]

[Phone] [name]

[Email] [contact]

Date: 2018/2/22

Statistical analysis

All numerical variables were depicted in bar charts with mean. Differences in means between any two groups (hyper- vs. hypo-, normal- vs. hyper-, or normal vs. hypo- reactive group) were analyzed by Student's *t*-test. The Bonferroni test was used to calculate differences between regimens, and reactive levels. Two-tail and $p < 0.05$ was considered statistically significant for the Student's *t*-test, and two-tail and total $p < 0.05$ was considered statistically significant for the Bonferroni test. All plots and statistical analyses were performed using SAS 9.4 (SAS Institute Inc., Cary, NC, USA) and IBM SPSS 22.

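### A PRU of exactly 208 falls in none of the three reactivity groups, although the Protocol's PRU section counts it as HOTPR

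*Protocol*

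**What the plan says.** The Protocol (Methods, In subgroup 1) defines three reactivity groups from the PRU after 7 days of treatment:

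- "1) normal reactive (defined as PRU=85-207"
- "2) hyporeactive (defined as PRU>208"
- "hyper-reactive groups (defined as PRU < 85"

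The Protocol's PRU measurements section sets a further threshold at the same number, this time inclusive: "In this study HOTPR was defined as PRUs \geq 208 as recently described".

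The SAP (Statistical analysis) uses the three groups as its comparison arms: "Differences in means between any two groups (hyper- vs. hypo-, normal- vs. hyper-, or normal vs. hypo- reactive group", each pair tested by Student's t-test. It repeats no cut-offs and does not mention HOTPR.

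On size, the Protocol says: "This study enrolled 35 patients(subgroup 1 and subgroup 2". It does not give the number in each subgroup or in each reactivity group.

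**The concern.** A classification rule for analysis groups should place every possible value in exactly one group. Here the normal group stops at 207 and the hyporeactive group starts above 208, so 208 is left over. The same value meets the study's HOTPR definition. A patient at 208 would therefore have high on-treatment reactivity under one section and no reactivity group under another.

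The gap lies at the boundary of the hyporeactive group, which is the group named in the study title and enters two of the SAP's three pairwise comparisons (hyper- versus hyporeactive, normal versus hyporeactive). A patient at 208 would either drop out of those tests or be assigned by a decision that no document records. With 35 patients spread over two subgroups and three reactivity groups, one patient can be a noticeable share of a group. The SAP is dated 2018/2/22, after the approved study period ended on 12/31/2017, so such a decision could have been taken with the data in hand.

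**Working it through.** **Step 1. Apply the printed rules to the values around each boundary.** All cut-offs come from the Protocol: the three groups from Methods, In subgroup 1, and HOTPR from PRU measurements.

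| PRU | Hyper-reactive (<85) | Normal (85–207) | Hyporeactive (>208) | HOTPR (≥208) |
|---|---|---|---|---|
| 84 | yes | no | no | no |
| 85 | no | yes | no | no |
| 207 | no | yes | no | no |
| 208 | **no** | **no** | **no** | **yes** |
| 209 | no | no | yes | yes |

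Running every integer from 0 to 600 (a range assumed for the check) through the rules gives the same picture. Only 208 falls in no group, no value falls in two, and 208 is the only value that is HOTPR but not hyporeactive. The lower boundary closes properly. The documents do not say that PRU is recorded as an integer. If decimals were kept, the gap would run from just above 207 up to and including 208.

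**Step 2. Look for text that closes the gap.** The SAP gives no thresholds, and no other section says how 208 is handled.

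**Step 3. Test the study's own inclusive sign.** If the hyporeactive boundary were read as ≥208, as in the HOTPR definition, every integer from 0 to 600 would fall in exactly one group. This is a consistency check only. It does not show what the sponsor intended.

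**Step 4. Judge how likely it is that a patient is affected.** The documents give no figure to reproduce and no PRU distribution, so the following inputs are assumptions: integer PRU, approximately normal, SD 50–80, and mean either 150–208 or, more widely, 120–208. The total of 35 is from the Protocol. The rule is written under subgroup 1, whose size is not given, so 15–20 patients are assumed for it.

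The probability of 208 for one patient is p = Φ((208.5 − mean)/SD) − Φ((207.5 − mean)/SD).

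- Mean 150, SD 80: p = 0.00383 (lowest for mean 150–208)
- Mean 120, SD 50: p = 0.00170 (lowest for mean 120–208)
- Mean 208, SD 50: p = 0.00798 (highest in both ranges)

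The probability of at least one such patient among n is 1 − (1 − p)^n. For n = 35:

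- 1 − (1 − 0.00383)^35 = 0.126
- 1 − (1 − 0.00170)^35 = 0.058
- 1 − (1 − 0.00798)^35 = 0.244

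| n | Mean 150–208 | Mean 120–208 |
|---|---|---|
| 35 | 12.6–24.4% | 5.8–24.4% |
| 20 | 7.4–14.8% | 3.3–14.8% |
| 15 | 5.6–11.3% | 2.5–11.3% |

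The expected number of patients at 208 among 35 is 35 × 0.00170 = 0.06 to 35 × 0.00798 = 0.28. The chance that nobody is affected is about 76–94% for 35 patients and 85–97% for 15–20.

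**The case against.** The strongest reply is that this is a slip of one character with an obvious meaning. A normal group ending at 207 makes sense only if the next group starts at 208, and the PRU measurements section uses that inclusive boundary. The Protocol is loose with strict signs elsewhere too: under Western blotting, samples above a WBC-to-platelet ratio of 0.4% are re-spun until they fall below it, which leaves exactly 0.4% unaddressed. The sign may also have been lost when the PDF was read. An inclusive sign survived in one place, but that does not prove the other was read correctly. All of this is fair. It makes the likely intention readable, but no current text states it.

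A second reply is that HOTPR is never equated with hyporeactive, so the two sections need not contradict each other. That is correct, and the link between the terms is an inference. The gap within the three-group rule does not depend on it.

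A third reply is that the effect is trivial and the probabilities rest on assumed inputs, the upper figure coming from a distribution centred exactly on 208 with the smallest SD considered. This also stands: the ranges show an order of magnitude and are not evidence from the trial. No estimate or conclusion has been shown to change.

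Finally, adding cut-offs to the SAP now would not pre-specify anything. That is true, and it is why the data check matters more than the wording.

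**Conclusion.** The concern holds on the text as printed: the three groups do not cover an integer PRU of 208, the Protocol's own HOTPR definition includes that value, and the SAP does not resolve it. The practical effect is small. It is confined to one integer value, and under the assumptions stated above it is more likely than not that no patient is affected; the documents do not show whether any was. It still deserves correction, because the threshold decides who enters the hyporeactive group and the remedy is almost free. Two things remain uncertain: whether the sign in the source protocol is as printed here, and whether HOTPR and hyporeactive are meant to be the same group.

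**What to change.** - Reconcile the group definitions in Methods with the HOTPR definition in PRU measurements, so that the analysis groups are exhaustive and mutually exclusive. Using the study's own inclusive boundary of 208 for the hyporeactive group would achieve this for integer values. The sponsor should confirm whether that was intended.
- State the cut-offs in the SAP, and say whether HOTPR and hyporeactive denote the same group and whether PRU is recorded as an integer.
- Check whether any patient had a PRU of exactly 208 (or between 207 and 208 if decimals were kept), and report how that patient was classified.

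The cost is one clarifying sentence in the SAP and one query of the data set. A change to the Protocol wording would also need ethics committee approval, since the certificate says "Any change should not be executed until being approved by TCHREC". As the approved period ended on 12/31/2017, the SAP sentence and the data check are the practical steps. The sentence should be presented as a clarification made after the event.

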TITLE OF STUDY

Downstream molecular signals of P2Y12 receptors in hyporeactive patients under clopidogrel treatment

NCT03190005 Unique Protocol ID: TCHIRB-10603117-E

PRINCIPAL INVESTIGATOR

[Name] [name]

[Department] Taipei City hospital Division of Cardiovascular section

[Address] [name]

[Phone] [name]

[Email] [contact]

Date: 2018/2/22

Statistical analysis

All numerical variables were depicted in bar charts with mean. Differences in means between any two groups (hyper- vs. hypo-, normal- vs. hyper-, or normal vs. hypo- reactive group) were analyzed by Student's *t*-test. The Bonferroni test was used to calculate differences between regimens, and reactive levels. Two-tail and $p < 0.05$ was considered statistically significant for the Student's *t*-test, and two-tail and total $p < 0.05$ was considered statistically significant for the Bonferroni test. All plots and statistical analyses were performed using SAS 9.4 (SAS Institute Inc., Cary, NC, USA) and IBM SPSS 22.

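### The SAP names no pairing or patient effect for regimen contrasts, although the treated and untreated samples very probably share patients; run as independent samples, these contrasts would be conservative and could lose power

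*SAP*

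**What the plan says.** The Statistical analysis section of the SAP assigns Student's t-test to pairwise comparisons of the three reactivity groups. For regimens it says only: "The Bonferroni test was used to calculate differences between regimens, and reactive levels". The significance level is two-sided, with a total of 0.05 over the Bonferroni family. The number of comparisons is not given, and no paired test, repeated-measures term, patient effect or unit of analysis appears.

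The protocol's Methods section describes the material:

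- Sample: "This study enrolled 35 patients(subgroup 1 and subgroup 2) who had undergone elective PCI and stent implantation". The split between subgroups, or between reactivity groups, is not given.
- Source: "Blood samples were obtained from all study patients, and platelets were separated as previously described".
- Treatment: "in-vitro experiments were performed using platelet-rich plasma (PRP) samples which were treated with different combinations of drugs". Five agents are then listed, with a no-drug control.
- Assay: "Total protein was prepared from untreated and treated samples, and subjected to Western blotting according to standard protocols".
- Crossing with reactivity group: "The Western blot responses were determined for each group after treatment with the different drugs".

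For layout, the protocol points to Supplementary Figure A, which is not in the supplied text.

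**The concern.** The regimens are applied to samples in the laboratory, not assigned to patients. In such an experiment each patient's plasma is normally divided over the conditions, so each patient acts as his or her own control. Comparing two regimens within patients removes the variation between patients; an analysis for independent samples leaves it in the error term.

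At stake are the contrasts that show which downstream signal responds to which inhibitor. With few patients and a Bonferroni penalty, a real response could be reported as absent.

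**Working it through.** **1. The plan's own figure.** The only number is 35 patients. It has no derivation, and no effect size, SD, power or within-patient correlation is given, so there is nothing to reproduce.

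**2. Do samples share patients?** Count the cells.

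- Five agents each used alone, plus control: 6 conditions × 3 groups = 18 cells; 35/18 = 1.9 patients per cell with one aliquot each.
- If the agents are ingredients, for example ADP with each of the other four, plus control: 5 × 3 = 15 cells; 35/15 = 2.3.
- Both are upper limits if subgroup 2 takes some of the 35. If subgroup 1 had 18 patients (assumed), 18/18 = 1.0.

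Cells this small would hardly support the planned t-tests, so several aliquots per patient is much the likelier layout.

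**3. What ignoring the patient does.** Let σ be the total SD, ρ the correlation between two aliquots of one patient, and n the patients per contrast.

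- True variance of a regimen difference: 2σ²(1 − ρ)/n.
- Variance assumed for independent samples: 2σ²/n.

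At ρ = 0.5 the assumed standard error is 1/√(1 − 0.5) = 1.41 times too large. The error is on the conservative side.

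**4. Size.** Assumptions: six conditions, all 15 pairs, per-comparison alpha 0.05/15 = 0.0033, equal variances and correlations. n = 12 is about 35/3 = 11.7, the most a reactivity group can average. n = 35 is the ceiling if regimens are compared over all patients.

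With a patient effect, power follows a noncentral t with df = (6 − 1)(n − 1) and noncentrality d√(n/(2(1 − ρ))), where d is the difference in SD units. For n = 12 and d = 0.8, df = 55 and the critical value is 3.07.

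- ρ = 0.5: 0.8 × √(12/1) = 2.77, power 39%.
- ρ = 0: 0.8 × √(12/2) = 1.96, power 15%.

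Power without the patient effect comes from simulation; simulated power with it agrees with the formula to about one point.

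| n | Effect (SD) | ρ | Power without patient effect | Power with patient effect |
|---|---|---|---|---|
| 12 | 0.8 | 0 | 15% | 15% |
| 12 | 0.8 | 0.3 | 12% | 25% |
| 12 | 0.8 | 0.5 | 9% | 40% |
| 12 | 0.8 | 0.8 | 6% | 90% |
| 12 | 1.5 | 0.5 | 79% | 98% |
| 12 | 2 | 0.5 | 99% | 100% |
| 35 | 0.8 | 0.5 | 70% | 96% |
| 35 | 1.5 | 0.5 | 100% | 100% |

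**5. False positives.** At n = 12, simulated family-wise error without a patient effect falls from 3.7% at ρ = 0 to 0.2% at ρ = 0.5. With a patient effect it stays at 3.6 to 3.8%. Neither exceeds 5%.

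**6. One contrast at p < 0.05.** For n = 12 and 0.8 SD, unpaired power is 46 to 47% for ρ from 0 to 0.5. A paired t-test gives 43%, 57% and 71% at ρ = 0, 0.3 and 0.5; it starts to help at about ρ = 0.1. For n = 35 and ρ = 0.5 the figures are 97% and 99.6%.

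**The case against.** The strongest reply is that the harm needs two things, neither of them written down: aliquots that share patients, and an analysis that ignores this. A reader might infer that the SAP treats aliquots as independent. It does not say so; it is silent, and Bonferroni adjustment fits paired and unpaired contrasts alike. Supplementary Figure A may show the layout, though it need not settle which test was used. This stands, and it makes the power loss conditional.

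The condition count is also uncertain. It is tempting to say at least six conditions, but the listed agents may be components of combinations. This too stands; step 2 shows that the inference survives with five.

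Third, drugs applied directly to plasma may produce large effects, and regimens may be compared over all patients. In either case the loss shrinks or disappears, as the table shows.

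Finally, the title question concerns hyporeactive patients and rests mainly on the group comparisons. The natural reading of the protocol is that groups are compared within one drug condition, with one value per patient, and those t-tests are sound. A reader might infer that the group comparisons carry inflated error because aliquots were pooled over regimens. The documents state no such pooling, so that charge is not made here.

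What remains is more than a missing detail. An analysis that takes account of the patient is better suited to the probable design than the method as written, and a mixed model gives up almost nothing if the correlation is zero.

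**Conclusion.** The point holds in conditional form, with minor to moderate severity. The SAP's omission is plain. That samples share patients is very probable but inferred. If the contrasts are run as for independent samples, they are conservative: the documents give no ground for inferring false drug effects, and the risk is missed ones. For moderate effects (0.8 SD), about 12 patients per contrast and correlation 0.5, power falls from about 40% to 9%. The loss is nil at zero correlation, slight at 2 SD, and absent at n = 35 with 1.5 SD. Effect size, correlation, patients per contrast and the 15-pair family are all assumptions; the documents supply none of them.

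**What to change.** State that the patient is the unit of analysis, how many aliquots each patient contributes, and which regimen contrasts are planned. Take the contrasts from one linear mixed model per readout, with group, regimen, group-by-regimen and a random patient effect, or from paired t-tests. Adjust by Bonferroni over the listed contrasts. Pair only where both conditions come from the same patients: the protocol also mentions controls who may be other people ("PRU values were determined for control patients and for patients treated with DAPT after 7 days of treatment"), and any contrast with them stays unpaired. Give the same particulars for subgroup 2, where the protocol says "In this subgroup 2, we developed an ex-vivo system to investigate the role of P2Y12 signaling on HOTPR". The within-regimen group t-tests can stay.

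The cost is a few lines in SAS or SPSS, both already named, and a data set that links each aliquot to its patient. The ethics certificate's study period ended on 12/31/2017 and the SAP is dated 2018/2/22 and written in the past tense, so re-analysis may be needed. If the correlation is near zero, paired t-tests lose a few points of power (n = 12, 0.8 SD, one contrast: 46% to 43%). The mixed model loses almost none, but assumes similar variance and correlation across regimens. If the contrasts were in fact paired, a sentence saying so would settle the pairing question.

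### Holm's step-down procedure would hold the SAP's total 5% error within the same family and find more of the second and later differences than plain Bonferroni

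*SAP*

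**What the plan says.** The SAP's Statistical analysis section assigns the multiplicity-adjusted comparisons to one method: "The Bonferroni test was used to calculate differences between regimens, and reactive levels". The criterion is "two-tail and total $p < 0.05$ was considered statistically significant for the Bonferroni test". No Holm or other stepwise version is named. The term single-step does not appear either, but Bonferroni without qualification is single-step: every one of m comparisons is judged at 0.05/m.

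The same section also covers the three reactivity pairs by Student's t-test: "Differences in means between any two groups (hyper- vs. hypo-, normal- vs. hyper-, or normal vs. hypo- reactive group". Each pair is judged at p < 0.05 with no adjustment stated.

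On numbers, the Protocol's Methods section says "This study enrolled 35 patients(subgroup 1 and subgroup 2", and sorts patients into three PRU groups whose sizes are not given. It lists five drugs and an untreated control, with platelet "samples which were treated with different combinations of drugs". The number of regimens to be compared is not stated. Nor does the SAP say how many comparisons the total of 0.05 covers.

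**The concern.** The SAP's stated aim is a total error of 5%. Plain Bonferroni meets it, but it keeps the strictest threshold for every comparison even after some nulls have been rejected. Holm relaxes the threshold after each rejection and meets the same aim. With at most 35 patients over two subgroups and three reactivity levels, power is scarce, and the single-step rule gives some of it up without any gain in error control. At stake is how complete the findings are: whether the study can show that a group differs from both others, or that several regimens differ from control, rather than only the single clearest difference.

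**Working it through.** **1. The SAP's own figure.** Bonferroni gives m × (0.05/m) = 0.05. For three reactivity pairs this is 3 × 0.0167 = 0.05. For six conditions (five drugs plus control, an assumption) there are 6 × 5/2 = 15 pairs, and 15 × 0.0033 = 0.05. The stated total is reproduced for any m.

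**2. The two rules.** Order the p-values p(1) ≤ … ≤ p(m).
- Bonferroni rejects every p ≤ 0.05/m.
- Holm compares p(1) with 0.05/m, p(2) with 0.05/(m−1), and so on up to p(m) with 0.05, and stops at the first failure.

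For m = 3 the Holm thresholds are 0.0167, 0.025 and 0.05, against 0.0167 throughout. The first threshold is identical, so the chance of at least one rejection is identical. The later ones are looser, so Holm rejects everything that Bonferroni rejects. It needs no independence, which matters if regimens are compared on platelets from the same patient.

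**3. Assumptions for size.** The documents give no effect sizes, SDs or group sizes. Assumed: normal data, SD 1, two-sided tests (pooled-variance t between groups, paired t against control), evaluated by simulation.

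**4. Three reactivity groups, m = 3.**

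| Setting | Measure | Bonferroni | Holm |
|---|---|---|---|
| 12/12/11, all means equal | familywise error | 4.4% | 4.4% |
| 12/12/11, one group 1.2 SD away | familywise error | 1.7% | 3.3% |
| same | power per true contrast | 61% | 65% |
| same | both true contrasts found | 45% | 53% |
| same | at least one rejection | 77% | 77% |
| 12/12/11, means 0/1/2 SD | all three found | 14% | 34% |
| 20/10/5, smallest group 1.2 SD away | power per true contrast | 39% | 42% |

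**5. Five regimens against control, m = 5, n = 12, paired effects of 0.9 SD.** Bonferroni uses 0.05/5 = 0.01 throughout.

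| Real effects | Correlation of differences | All found, Bonferroni | All found, Holm |
|---|---|---|---|
| 1 of 5 | 0 | 53% | 53% |
| 3 of 5 | 0 | 15% | 24% |
| 3 of 5 | 0.5 | about 26% | about 35% |
| 5 of 5 | 0 | 4% | 29% |
| 5 of 5 | 0.5 | 16% | 45% |

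The five differences share one control, so the correlated rows are the more realistic ones.

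**6. All 15 regimen pairs, n = 12 each, treated as independent groups.** Average power per true difference rises from 0.390 to 0.410, from 0.388 to 0.429 and from 0.394 to 0.434 in three patterns of means.

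**7. The unadjusted t-test rule, for comparison.** In the 12/12/11 setting with one group 1.2 SD away, testing each pair at 0.05 gives 78% power per true contrast. With all means equal, its familywise error is about 12%.

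**The case against.** Bonferroni is a valid choice that holds its stated error, so nothing here is a mistake. The gain in average power is about 2 to 9 points, and nil when only one effect is real. The 12/12/11 split is a best case, since the 35 patients cover both subgroups. All of that stands, and it limits this point to efficiency.

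The adjacent t-test rule is the stronger objection. It already gives the three reactivity pairs a more liberal route to significance, so naming Holm changes little for them while that route stays open. This also stands: the change is useful for those contrasts only if the SAP makes the adjusted rule govern.

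A reader might go further and apply Shaffer's modification (0.05/3 first, then 0.05 for the other two), which gives 70% per true contrast in the 12/12/11 setting. It works because, once one pair truly differs, at most one of the other two equalities can hold. But that logic needs a family of exactly the three pairwise contrasts on one readout. The Protocol's Western blotting section lists many proteins, and its Methods section several drug conditions. The SAP does not define the family so narrowly, so the documents do not support Shaffer's thresholds as a general replacement.

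A reader might also give the regimens 0.05 and the reactivity contrasts another 0.05. The SAP puts both under one Bonferroni test with one total. If that total covers both, two separate allowances could give 1 − 0.95² = 9.75% with independent families and all nulls true. Part of any apparent gain would then be extra alpha.

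**Conclusion.** The point holds as an efficiency improvement. Within whatever family the SAP's total of 0.05 covers, Holm keeps the 5% and never rejects less than Bonferroni. Under the assumed effects the gain is about 4 points per true contrast and 7 to 8 points for finding both (12/12/11, one group 1.2 SD away), and about 9 to 10 points for finding all of three real regimen effects. These sizes depend on effects, SDs, group sizes and correlations that the documents do not give; that Holm is never worse does not.

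It does not follow that the SAP's error control fails, that a first significant result becomes more likely, or that the larger gains with all effects real are typical. The change ranks below two matters that the SAP must settle anyway: which comparisons form the family, and which test governs the reactivity contrasts.

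**What to change.** In the SAP's Statistical analysis section:
- Replace the Bonferroni test with the Holm step-down procedure at total two-sided 0.05, applied within the family that the SAP's total covers. Write that family down. Do not give regimens and reactivity contrasts 0.05 each unless the SAP defines them as separate families.
- State that this rule governs the three reactivity contrasts in place of the unadjusted t-test threshold.
- Report Holm-adjusted p-values: the j-th is the largest of (m − i + 1) × p(i) over i ≤ j, capped at 1.
- Allow Shaffer's modification only where a family is exactly the three pairwise reactivity contrasts on one readout.

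The cost is a sentence or two of text and a few lines of code, with no patients or assays. There are two downsides. Simultaneous confidence intervals that match Holm are less simple, though the SAP plans none. Timing also matters: the SAP is dated 2018/2/22, after the ethics certificate's study period ended on 12/31/2017. The documents do not say whether results were known by then. A switch made after results are known should be labelled post hoc and shown beside the Bonferroni results.
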